1.2.6 Rationale for Re-Induction

Re-treatment with Anti-CTLA-4 agent provide durable response or stable disease in patients with melanoma who initially respond to treatment but later progressed^{26,27} with some subjects achieved better overall response after re-induction⁴. No new types of toxicities observed after re-

induction with safety profile consistent with induction profile.^{26,27} These findings support re-treatment with immune checkpoint inhibitors after initial disease control.

RFA or TACE are modalities inducing localized cell death and enhancing antitumor immune response^{28,29}. To date it is unknown what type of treatment, RFA vs TACE is more immunogenic. By allowing the same patient to undergo TACE and RFA we will produce different immune stimulation and possibly enhance antitumor immune response. In addition, benefit of re-treatment with TACE or RFA is to provide a similar immune boost as revaccination treatment in cancer vaccine clinical trials.

Combining TACE and RFA in HCC treatments has been attempted in single centers small studies showing an improvement in OS without significant increase in side effects^{30,31}. Larger randomized clinical trial of 189 patients resulted in improvement in OS and recurrence free survival in RFA-TACE group relative to RFA group alone without significant differences in toxicity profiles.³² Findings from these studies confirm tolerability of combination. For definite conclusions on efficacy of combined interventional management larger clinical trials are needed.

1.2.7 Rationale for Viral Hepatitis Studies and Specifically for Hepatitis B Surface Antigen and Hepatitis B Immune Monitoring

Anti-HCV specific immune responses as well as a reduction in Hepatitis C viral load have been described in patients with chronic HCV infection and HCC (decline in serum HCV viral load from median values: basal 3.78×10^5 copies/ml to median values on day 120 of 3.02×10^4 copies/ml, $p=0.02$; vs. day 210 1.69×10^3 copies/ml, $p=0.04$); in addition three patients demonstrated a complete viral response for the duration of the follow-up³³.

The antiviral effect of CTLA-4 blockade in patients with chronic HBV infection is unknown. Hepatitis e antigen (HBeAg) is a marker of viral replication and infectivity that is usually associated with active liver disease. Hepatitis B surface antigen (HBsAg) is a protein on the surface of the hepatitis B virus. Its presence identifies patients with chronic infection. CTLA-4 blockade in cynomolgus macaques enhanced antibody response to hepatitis B surface antigen (HBsAg)³⁴. Interestingly, polymorphisms of CTLA-4 have been associated with chronic hepatitis B and C infection^{35,36}. The mechanisms behind these events imply an existing link between CTLA-4 activity and hepatic viral pathogenesis that should be exploited in details for therapeutic benefit. The population of HCC patients with chronic hepatitis B virus (HBV) infection will provide an exceptional occasion to simultaneously test the anti-tumoral, immune and antiviral effect of tremelimumab.

1.2.8 Rationale for Amendment F

The purpose of amendment F is to add 3 additional patient cohorts (denoted C, D and E) of N=10 patients each to evaluate additional globally used and potentially immunomodulative procedures (cryoablation and external beam radiation) in patients with HCC. We would also like to evaluate RFA plus tremelimumab in biliary tract carcinoma. The justification for each of these cohorts is as follows:

Cohort C: SBRT plus tremelimumab in HCC (removed, effective with amendment I). Several studies have documented an increase in peripheral antitumor immunity following radiation. It may even be the case that an intact immune system is critical for RT to exert its maximal antitumor effect. This was suggested by a mouse model of melanoma in which single-fraction

RT slowed the growth of small tumors in immune-competent but not immune-deficient mice³⁷. The same authors also showed that in an animal model of breast cancer ablative RT of a primary tumor prevented the growth of metastatic tumor colonies in the lung, an effect that was dependent on the presence of CD8⁺ T cells. Other animal models have likewise displayed augmentation of systemic antitumor immunity following local RT³⁸⁻⁴⁰. The underlying mechanism appears to be that RT-induced necrosis results in the exposure of tumor antigens, thereby increasing the pool of intracellular peptides for cross-presentation⁴¹. Radiation has been shown to augment MHC-I expression by tumors, which is critical for antigen recognition by cognate CD8⁺ TCRs and which is known to be diminished in tumors as one of their escape mechanisms⁴². Tumor antigen processing and presentation on MHC-I molecules is dependent on expression of a protein called highmobility group box 1 (HMGB-1), a “danger signal” which binds toll-like receptor 4 (TLR4) on dendritic cells. In a pivotal study Apetoh et al. demonstrated that RT causes dying tumor cells to release HMGB-1⁴³. Intriguingly these authors also reported that in breast cancer patients undergoing radiation and chemotherapy the presence of a polymorphism in TLR4 – and by implication a less immunogenic drug-induced cell death – was associated with an inferior prognosis. Similarly, in esophageal cancer patients preoperative chemoradiation has been shown to increase cancer-specific T cell responses and serum levels of HMGB-1, the latter of which correlated with overall survival⁴⁴.

Despite this, only a few cases of spontaneous decrease of metastases following radiation – the so-called abscopal effect – have been reported. This is presumably because the immune response by itself is too weak to be clinically significant. A number of studies have tried to boost this anti-tumor immune response following ablation by combining with an immunomodulatory agent: Dewan et al. evaluated RT in combination with anti-CTLA-4 antibody in two separate mouse models of breast and colorectal carcinoma⁴⁵. The authors found that the combination of anti-CTLA4 and RT achieved enhanced tumor response at the primary site (compared to either modality alone). in addition to an abscopal effect. (Interestingly this only occurred in fractionated versus single-dose RT). The frequency of CD8⁺ T cells showing tumor-specific IFN-gamma production was proportional to the abscopal effect. Demaria et al. tested the combination of RT with CTLA-4 blockade in a breast cancer model (4T1) known to be poorly immunogenic⁴⁶. Anti-CTLA4 alone did not have any effect on primary tumor growth or survival. RT was able to delay the growth of the primary irradiated tumor, but in the absence of anti-CTLA4 survival was similar to that of control mice. In contrast, mice treated with RT + anti-CTLA4 had a statistically significant survival advantage. The increased survival correlated with inhibition of lung metastases formation and required CD8⁺.

Administering radiation therapy to the liver is not standard or conventional. With newer techniques however, this has been shown to be a safe strategy and to have palliative benefit in an incurable population. For example, [name] – one of our associate investigators – has previously conducted a study employing hepatic radiation in colorectal cancer⁴⁷. In that study patients received a total radiation dose of 32 Gy to sites of metastatic disease in the liver, delivered in 8-Gy courses (4 separate 2-Gy fractions) beginning one day after each vaccine boost (days 22–25, 36–39, 50–53, 64–67). The treatment was well tolerated, with the most common toxicity being a transient dermatologic reaction as a result of the vaccine used in the study. There were no \geq grade 3 toxicities attributable to the treatment and specifically there were no \geq grade 2 hepatic toxicities. Other additional reports have documented the safety of SBRT to the liver at doses/schedules of 60 Gy/10 Fr and 50 Gy/4 Fr⁴⁸; 36 to 60 Gy in 6 to 15 Gy per fraction (HCC, cholangio and colorectal cancer)⁴⁹; single doses of 17 to 30 Gy (median dose 24 Gy)⁵⁰; median

dose per fraction and total dose of 3.6 Gy (2.0-13.0 Gy) and 55 Gy (30-80 Gy) in N=26 patients with colorectal cancer⁵¹.

Cohort D: Cryoablation and tremelimumab in HCC. Whilst RFA is the more traditional ablative strategy in HCC there is a growing use of cryoablation globally. In addition there is a growing body of data which suggests that it may be more effective⁵². At a minimum it appears to be equivalent in terms of safety and efficacy, as recently shown in a recent multicenter randomized study comparing the outcomes of percutaneous cryoablation with RFA for the treatment of HCC⁵². Three hundred and sixty patients with Child-Pugh class A or B cirrhosis and one or two HCC lesions ≤ 4 cm, treatment naïve, without metastasis were randomly assigned to cryoablation (n=180) or RFA (n=180). The primary end-points were local tumor progression at 3 years after treatment, and safety. Local tumor progression rates at 1, 2, and 3 years were 3%, 7%, and 7% for cryoablation and 9%, 11%, and 11% for RFA, respectively (P=0.043). For lesions >3 cm in diameter, local tumor progression rate was significantly lower in cryoablation group versus RFA group (7.7% vs 18.2%, P=0.041). The 1-, 3-, and 5-year overall survival rates were 97%, 67% and 40%, for cryoablation and 97%, 66%, and 38% for RFA, respectively (P=0.747). The 1-, 3-, and 5-year tumor-free survival rates were 89%, 54%, and 35% in cryoablation group and 84%, 50%, and 34% in RFA group, respectively (P=0.628). Major complications occurred in seven patients (3.9%) following cryoablation and in six patients (3.3%) following RFA (P=0.776). The conclusions of this study were that cryoablation appeared to be just as safe and feasible as radiofrequency or microwave ablation in HCC and is very commonly used across the world. Intriguingly – for our purposes - there is evidence that cryoablation may be better in terms of immune stimulation compared to other ablative strategies⁵³.

Cohort E: RFA in biliary tract carcinoma: Biliary tract carcinoma (BTC) is the second most common hepatobiliary cancer. For the majority of patients who present with or develop metastatic/ unresectable disease the modest standard therapy comprises Gemcitabine in combination with cisplatin based on the ABC-02 trial which demonstrated a median overall survival benefit of 11.7 v 8.1 months (P<0.001) in favor of cisplatin–gemcitabine compared to gemcitabine alone⁵⁴. There is no standard second-line treatment for biliary tract carcinomas.

The most compelling argument in favor of testing immune-based strategies (and anti-PD1 therapy in particular) in this disease is that chronic inflammation is the most common etiologic factor in the development of BTC. Recent studies have linked the increasing incidence of chronic hepatitis C virus infection with intrahepatic cholangiocarcinoma⁵⁵, which may explain the increasing incidence of the intrahepatic subtype⁵⁶. In biliary tract cancer, the prevalence and prognostic relevance of infiltrating T-lymphocytes has been documented. Goepfert et al. evaluated immune cell infiltration in 375 cases of biliary tract cancer obtained following surgical resection⁵⁷. Approximately half the patients had intraepithelial tumor infiltrating T cells (both CD4 and CD8) and this was associated with better survival. Further evidence of the importance of immune activation/suppression, this time specific to the PD1/PD-L1 axis, was provided by Ye et al. who evaluated the expression of B7-H1(PD-L1) and its receptor PD-1 in N=31 surgically resected cholangiocarcinoma tissues and the corresponding cancer adjacent tissues⁵⁸. Expression of PD-L1 and PD-1 was found to be up-regulated in cholangiocarcinoma tissues compared with the cancer adjacent tissues. Tumor-related PD-L1 expression was significantly correlated with both tumor differentiation and pTNM stage and was inversely correlated with CD8+ tumor-infiltrating lymphocytes. Similarly, Nakakubo et al. investigated the significance of tumor-infiltrating immune cells in 110 surgically resected biliary tract cancer (gallbladder) specimens⁵⁹.

They found high levels of CD4+ T cell (51.1%), CD8+ T cell (37.8%), NL cell (33.3%), and dendritic cell (48.9%) infiltration. CD4+ and CD8+ T cell infiltration correlated with decreasing tumour invasion, and high numbers of infiltrating DCs correlated with decreasing lymph-node tumour metastasis. Furthermore, increased infiltration of CD4+ and CD8+ T cells and DCs exhibited a significant correlation with prolonged survival. Because of these data, and coupled to the data summarized earlier for immune stimulation following RFA, we wish to treat a cohort of biliary tract carcinoma patients.

1.2.9 Rationale for Amendment I

The purpose of amendment I is to remove Cohort C. Given a range of factors - the number of variables in this study, the finding of interesting activity with ablative methods (commonly used in HCC) and the relative infrequency of SBRT in this disease – it was decided both scientifically and for patient safety reasons to focus and refine our research efforts. At this point we will not enroll to Cohort C but preferentially enroll HCC patients to either cohort B of this protocol or our new protocol (16-C-0135). Should we decide to evaluate SBRT in combination with immune modulating therapy in this population in the future it will only be done after an IRB amendment.

1.2.10 Rationale for Amendment J

The purpose of amendment J is to stop further tremelimumab treatment beyond 2 years if there is no evidence of disease progression. Currently patients would continue to receive tremelimumab treatment every 12 weeks until disease progression. The justification for this is as follows:

1) Two-year-duration of immune checkpoint inhibitor treatment is adequate for disease treatment and control: early trials in melanoma allowed treatment until progression; then, 2-year duration was the maximal adopted by majority of clinical trials^{60, 61, 62} and approved regimens. Such study design does not prevent patients from benefiting the most from immune checkpoint inhibitor treatment⁶³. Effectively, the discontinuation of immune checkpoint inhibitor after a predetermined duration is not associated with an increased risk of acquired resistances such as that described with cytotoxic chemotherapy⁶³. Few reports have examined the outcome in patients who achieved a response and stopped therapy after 2 to 3 years⁶⁴. Among them, 61 (64%) stopped treatment after complete response and maintained their remission. Median duration of treatment was 23 months. Only 2 of the 61 patients who stopped treatment after complete response experienced disease progression. Many of those who did not achieve a complete response and whose disease progressed were able to respond to further immunotherapy⁶⁴. The existence of the “tail on the curve” of survival in melanoma, and now other cancers, suggests that a subset of patients who discontinue treatment with one of these agents experience durable responses after therapy and do not need to be treated until progression. Presumably, the patient’s immune system has been engaged and is still monitoring and effectively suppressing the cancer. Nevertheless, re-challenging the tumor with the same immune checkpoint inhibitor even after a long stable period demonstrated a greater response and lesser adverse events⁶⁵. Thus, indefinite treatment may not be truly necessary, and a duration of not less than 1 year and not more than 2 years seems reasonable.

2) Prolonged immune checkpoint inhibitor exposure has greater risks for potentially life-threatening toxicities: despite important clinical benefits, immune checkpoint inhibition is associated with a unique spectrum of immune-related adverse events. Serious side effects are observed in less than 10% of patients, and typically emerge an average of 6 to 12 weeks after the

start of treatment^{66, 67}. The risk of side effects increases with higher doses, and overall seems to increase with cumulative exposure. Moreover, as immunotherapies are being tested in combination, side effects tend to be additive. For example, the more common adverse effects are related to GI inflammation, which can be as minor as slight irritation or as severe as colitis, potentially even leading to perforation of the bowel. Those potentially life-threatening toxicities in the context of prolonged treatment may outweigh the benefits of indefinite immune checkpoint inhibitor therapy.

Given above discussed justifications, it is decided both scientifically and for patient safety reasons to focus and refine our research efforts. At this point we will discontinue tremelimumab administration after 2 years if patient is experiencing responding to the treatment over 2 years, including stable disease, partial or complete remission.

2 ELIGIBILITY ASSESSMENT AND ENROLLMENT

2.1 ELIGIBILITY CRITERIA

2.1.1 Inclusion Criteria

2.1.1.1 Patients must have histopathological confirmation of hepatocellular carcinoma (HCC) or (Cohort E only) biliary tract carcinoma (BTC) by the Laboratory of Pathology of the NCI prior to entering this study OR histopathological confirmation of carcinoma in the setting of clinical and radiological characteristics which, together with the pathology, are highly suggestive of a diagnosis of HCC (or biliary tract carcinoma in Cohort E). Fibrolammellar variant is also allowed. For cohort E, the term BTC includes intra- or extrahepatic cholangiocarcinoma, gallbladder cancer or ampullary cancer, as long as there is an intrahepatic component amenable to RFA.

2.1.1.2 Patients must have disease that is not amenable to potentially curative resection, transplantation or ablation. For Cohorts A and D patients must have progressed on, been intolerant to, or refused prior sorafenib therapy. Cohort E patients must have received at least one line of chemotherapy for BTC.

2.1.1.3 Disease must be technically amenable to transhepatic arterial chemoembolization (TACE), radiofrequency ablation (RFA), or cryoablation. Each case will be discussed at GI tumor board with interventional radiology. Patients must have evaluable disease.

2.1.1.4 If liver cirrhosis is present, patient must have a Child-Pugh A/B7 classification (see Appendix B section 12.2).

2.1.1.5 Age ≥ 18 years

2.1.1.6 Life expectancy of greater than 3 months.

2.1.1.7 ECOG performance status 0-2 (see Appendix A section 12.1)

2.1.1.8 Patients must have normal organ and marrow function as defined below:

leukocytes	$\geq 3,000/\text{mcL}$
absolute neutrophil count	$\geq 1,000/\text{mcL}$
platelets	$\geq 60,000/\text{mcL}$
total bilirubin	If cirrhosis present: Part of Child Pugh

	requirement If no cirrhosis: Bili should be ≤ 2 xULN
Serum albumin	If cirrhosis present: Part of Child Pugh requirement If no cirrhosis: albumin should be \geq 2.5g/dl
Patients are eligible with ALT or AST up to 5 x ULN.	
creatinine	<1.5X institution upper limit of normal OR
creatinine clearance	≥ 45 mL/min/1.73 m ² , as calculated below, for patients with creatinine levels above institutional normal

2.1.1.9 Patients must have recovered from any acute toxicity related to prior therapy, including surgery. Toxicity should be \leq grade 1 or returned to baseline.

2.1.1.10 Patients must not have other invasive malignancies within the past 5 years (with the exception of non-melanoma skin cancers, non-invasive bladder cancer or localized prostate cancer for whom systemic therapy is not required).

2.1.1.11 Patient must be able to understand and willing to sign a written informed consent document.

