3.9.3.1 Gastrointestinal

3.9.3.2 Liver (Immune-mediated hepatitis)

Tremelimumab can result in severe and fatal inflammation of the liver most commonly manifested as elevation of transaminases and hyperbilirubinemia. Liver enzymes and liver function tests (hepatic transaminase and bilirubin levels) will be evaluated and patients assessed for signs and symptoms of hepatitis before each dose of Tremelimumab.

In patients who experience AST or ALT > 5.0 ULN and/or baseline or total bilirubin > 3.0 ULN liver biopsy should be considered as per standard of care investigation for autoimmune hepatitis.

Symptoms	Immediate action	Subsequent management
Moderate • AST or ALT >2.5 to 5.0 ULN and/or baseline (if this was abnormal). • Total bilirubin >1.5 to 3.0 ULN	Withhold Tremelimumab • Rule out infectious or malignant causes • Increase frequency of liver function test monitoring until resolution	Symptoms resolve: Resume Tremelimumab if liver function tests are 2.5 ULN or return to baseline and bilirubin level is 1.5 ULN or returns to baseline IF AST OR ALT CONTINUES TO

		ELEVATE TO >5.0 ULN OR TOTAL BILIRUBIN >3.0 ULN, See management for ‘severe’
--	--	---

Symptoms	Immediate action	Subsequent management
Severe 
 • AST or ALT > 5.0 ULN and/or • Total bilirubin > 3.0 ULN 	Hold Tremelimumab and re-evaluate until toxicity improves to \leq grade 1 or pre-treatment baseline. Treatment will be discontinued in patients who experience grade 3 non-hematologic toxicities that do not resolve to grade 1 or baseline within 4 weeks. 
 • Increase frequency of liver function test monitoring until resolution • Administer systemic corticosteroid of 1 to 2 mg/kg/day of prednisone or equivalent. Consider liver biopsy as per standard of care investigation for autoimmune hepatitis 	Symptoms resolve: When liver function tests show sustained improvement or return to baseline, initiate corticosteroid tapering and continue to taper over 1 month Consider alternative immunosuppressive therapy Symptoms Ongoing >1 week: Consider alternative immunosuppressive therapy

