13.2 APPENDIX B: CHILD-PUGH CLASSIFICATION SYSTEM

Parameter	Points assigned		
	1	2	3
Ascites	Absent	Slight	Moderate
Bilirubin	<2 mg/dL (<34.2 micromol/liter)	2-3 mg/dL (34.2 to 51.3 micromol/liter)	>3 mg/dL (>51.3 micromol/liter)
Albumin	>3.5 g/dL (35 g/liter)	2.8-3.5 g/dL (28 to 35 g/liter)	<2.8 g/dL (<28 g/liter)
Prothrombin time			
Seconds over control	<4	4-6	>6
INR	<1.7	1.7-2.3	>2.3
Encephalopathy	None	Grade 1-2	Grade 3-4

Modified Child-Pugh classification of the severity of liver disease according to the degree of ascites, the plasma concentrations of bilirubin and albumin, the prothrombin time, and the degree of encephalopathy. A total score of 5-6 is considered grade A (well-compensated disease); 7-9 is grade B (significant functional compromise); and 10-15 is grade C (decompensated disease). These grades correlate with one- and two-year patient survival: grade A - 100 and 85 percent; grade B - 80 and 60 percent; and grade C - 45 and 35 percent.

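### With cirrhosis, one Child-Pugh B7 profile has no upper bilirubin limit at entry, so an eligible patient could, on a literal reading of 3.9.2, be stopped permanently without any worsening

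*Combined protocol and SAP*

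**What the plan says.** **Entry rules.** Section 2.1.1.8 sets hepatic limits in three ways.

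- Transaminases, all patients: "Patients are eligible with ALT or AST up to 5 x ULN".
- Bilirubin without cirrhosis: "If no cirrhosis: Bili should be ≤ 2 xULN".
- Bilirubin with cirrhosis: no number, only "If cirrhosis present: Part of Child Pugh" requirement.

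The Child-Pugh condition itself is in 2.1.1.4: "If liver cirrhosis is present, patient must have a Child-Pugh A/B7 classification". Appendix B grades a total of 5-6 as A and 7-9 as B, so B7 means a total of exactly 7. It gives bilirubin 3 points for any value above 3 mg/dL. The exclusion criteria in 2.1.2 add no bilirubin limit. Section 2.1.3.5 applies the same eligibility criteria again at re-induction.

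**On-treatment rules.** Section 3.9.3.2 requires liver tests before each dose. Its severe category includes "total bilirubin > 3.0 ULN". The actions are to hold drug until improvement to "grade 1 or pre-treatment baseline" or better, and "Administer systemic corticosteroid of 1 to 2 mg/kg/day of prednisone or equivalent". Section 3.9.2 requires permanent discontinuation when AST or ALT exceeds 8 x ULN or total bilirubin exceeds 5 x ULN. That row has no baseline reference and no relatedness condition. Other rows in the same table do carry one: diarrhea or colitis, other events of grade 3 or higher, and laboratory abnormalities of grade 3 or higher.

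**The concern.** An entry limit should lie at or below the stopping limit for the same measurement. Otherwise the protocol admits patients whom it must later stop for a value they brought with them. Transaminases and non-cirrhotic bilirubin meet this condition. Cirrhotic bilirubin does not, because the Child-Pugh total does not bound the bilirubin value.

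Two things are at stake, both for individual patients. A patient could be enrolled, exposed to tremelimumab, and then permanently stopped with no new liver injury, unless the investigator reads into 3.9.2 a baseline exemption that it does not state. Also, a baseline already above a fixed limit removes that limit's value as a signal of new hepatitis, in patients who already have cirrhosis.

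**Working it through.** No sample size, power or error rate is involved, and the plan has no figure of its own to reproduce. The check is a count of score profiles and a comparison of limits.

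**Inputs.** Five Child-Pugh items scored 1 to 3 each, and the bilirubin classes (Appendix B); maximum total 7 (2.1.1.4); entry limits (2.1.1.8); severe limits (3.9.3.2); permanent limits (3.9.2). The documents give no bilirubin ULN in mg/dL, so 0.8 to 1.5 mg/dL is assumed.

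**Step 1: eligible profiles.** The minimum total is 5, so at most 2 points can be added.

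- No added point: 1 profile.
- One added point: 5 profiles.
- Two added points: two items at 2 points (10 profiles) or one item at 3 points (5 profiles).
- Total: 1 + 5 + 10 + 5 = 21.

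Bilirubin scores 1 point in 15 of these, 2 points in 5 and 3 points in 1. The last is 3 + 1 + 1 + 1 + 1 = 7: no ascites, albumin above 3.5 g/dL, prothrombin time in the lowest class, no encephalopathy. It is B7 and eligible.

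**Step 2: the limits in mg/dL.**

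| Assumed ULN | 3 x ULN | 5 x ULN | 3 mg/dL as a multiple of ULN |
|---|---|---|---|
| 0.8 | 2.4 | 4.0 | 3.75 |
| 1.0 | 3.0 | 5.0 | 3.00 |
| 1.2 | 3.6 | 6.0 | 2.50 |
| 1.5 | 4.5 | 7.5 | 2.00 |

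The 3-point class has no upper end, so both limits can be exceeded at entry for every assumed ULN. At ULN 1.0 the whole 3-point class is above 3 x ULN. The other 20 profiles have bilirubin of at most 3 mg/dL. That never reaches 5 x ULN in this range, and does not exceed 3 x ULN when ULN is 1.0 or more. Below 1.0, the top of the 2-point class also passes 3 x ULN.

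**Step 3: stopping limit divided by entry limit.**

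| Measurement | Severe / entry | Permanent / entry |
|---|---|---|
| AST or ALT | 5.0/5 = 1.0 | 8/5 = 1.6 |
| Bilirubin, no cirrhosis | 3.0/2 = 1.5 | 5/2 = 2.5 |
| Bilirubin, cirrhosis | no entry limit | no entry limit |
| Bilirubin, cirrhosis, capped at 3 x ULN | 3.0/3 = 1.0 | 5/3 = 1.67 |

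**Step 4: follow the patient.** Take the 3-point profile, an assumed ULN of 1.0 mg/dL and a stable bilirubin just above 5.0 mg/dL. The patient is eligible and receives dose 1. Liver tests are due again before dose 2 at the latest. Bilirubin is unchanged and above 5 x ULN. The 3.9.2 row applies on its face and offers no release. Under the 3.9.3.2 severe row the same unchanged value passes the trigger, but already satisfies the release at pre-treatment baseline. There, only the trigger and the corticosteroid instruction lack a baseline reference.

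**The case against.** The strongest reply is that these are toxicity rules. Section 3.9.2 is headed as a list of toxicities, 3.9.3 concerns immune-mediated reactions to the drug, toxicity is evaluable only from first treatment (6.3.1.1), and 7.1.1 treats an existing abnormality as an adverse event only if it worsens. Section 3.9 also asks for other causes to be ruled out at onset of any toxicity. A sensible investigator could conclude that a stable cirrhotic bilirubin is not a toxicity at all.

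Much of this stands. A reader might infer that the patient already meets a stop rule before dose 1. The documents do not support that: an unexposed patient has no reaction to manage and nothing to discontinue. A reader might also put the severe row on the same footing as 3.9.2, but its hold ends at baseline. Nor does the precedence that 3.9 gives to specific immune-mediated rules strengthen the case. It covers immune-mediated reactions, which is the very point in question for a stable baseline, and it does not name 3.9.2.

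What does not stand is the view that nothing remains. The 3.9.2 bilirubin row omits the relatedness wording that other rows carry, so the literal reading is available and the exemption has to be supplied by the reader. Tumor-board review and the life-expectancy criterion are individual checks, but neither sets a bilirubin value.

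Using Child-Pugh for both bilirubin and albumin in cirrhosis is also a coherent design choice, and baseline wording in 3.9.2 would be a more direct repair. That is fair. It would, however, leave entry unbounded, and the fixed limits would still be uninformative about new injury in these patients.

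**Conclusion.** The point holds in a narrow form. One of 21 qualifying score profiles has no bilirubin ceiling at entry. Above 5 x ULN it conflicts with 3.9.2 read literally, from the first on-treatment liver check onward. Between 3 and 5 x ULN the conflict is limited to the trigger and the corticosteroid instruction of the severe row.

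The mg/dL values rest on the assumed ULN. The existence of the gap does not, because the class is open-ended. The figure of 1 in 21 counts score combinations and should not be read as a patient frequency. The documents give none, and the profile is probably rare.

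Two wider readings are not supported. The moderate row of 3.9.3.2 lets dosing resume at baseline, so it raises no comparable problem. In the severe row and in 3.9.2, bilirubin and transaminases do not differ in baseline wording. What differs is the entry limit.

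No endpoint, power or sample-size figure changes. Severity is minor: a cheap safety improvement.

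**What to change.** In the cirrhosis line of 2.1.1.8, keep the Child-Pugh requirement and add that total bilirubin must be no higher than 3 x ULN. State that this is checked on the baseline chemistry drawn within 72 hours before first dose (2.3.2). The screening chemistry in 2.2.2 has no stated time window, and neither section says that eligibility is rechecked on the later draw. Through 2.1.3.5 the cap also applies at re-induction. A patient meeting it on that draw starts at or below both bilirubin limits.

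The cost is one line of text and no new test. A few B7 patients become ineligible, including some at 3 to 5 x ULN for whom the severe row already allows release at baseline. At ULN 1.0 mg/dL the whole 3-point profile is excluded. At 1.2 or 1.5, those above 3.0 and up to 3.6 or 4.5 mg/dL stay eligible. If the local ULN is below 1.0, some 2-point patients are excluded too: at 0.9 the cap is 3 x 0.9 = 2.7 mg/dL. A patient entering just under the cap can still cross the severe limit with a small rise, as a patient with AST or ALT just under 5 x ULN can now.
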